5.1 Dose Specifications

Radiation treatments will meet all requirements considered standard clinical care. Patients should ideally be treated with 3 fractions of radiation but up to 5 fractions may be allowed if treating radiation oncologist is concerned with toxicity. All radiation treatments must complete within a 2 week period. Up to 3 sites may be treated concurrently. For neutron radiation, 2.8 Neutron Gy x 3 fractions is the goal dose, but may be decreased to 1.5 Gy x 3-5 fractions at discretion of treating radiation oncologist.

5.2 Localization, simulation, and immobilization

- All patients will undergo CT based treatment planning at initial simulation per standard clinical care. Immobilization devices will be used as applicable to treated anatomic region. The CT scan must capture the region of interest as well as surrounding organs at risk (OAR) with sufficient margin for treatment planning. The CT scan should be obtained with a uniform slice thickness of less than or equal to 3 mm throughout. The use of IV contrast is left to the discretion of the treating physician.
- All lesions with potential for respiratory motion should be evaluated by appropriate means including 4D CT scan and/or implanted fiducial marker(s). Respiratory motion management including but not limited to active-breathing control, respiratory gating, and fiducial marker tracking, will be employed for qualifying patients per standard clinical practice.
- Daily image guidance will be employed for target localization.

5.3 Target Volumes

- The gross tumor volume (GTV) is defined as all known gross disease encompassing the selected index lesion as visualized the planning CT scan and aided by additional diagnostic imaging studies (PET/CT or MRI). The use of additional diagnostic imaging studies is dependent on the location of the index lesion and is left to the discretion of the treating physician.
- An internal gross tumor volume (IGTV) is defined for mobile index lesions at the discretion of the treating physician. A 4-D CT scan will be acquired in order to account for the motion of the lesion during treatment. The IGTV will be defined as the union of the visualized index lesion on all gated CT data sets.
- The clinical target volume (CTV) can include a margin of 0-10 mm at the discretion of the treating physician.
- The planning target volume (PTV) will be defined as per standard of care.

5.4 Critical Structures

Organ at risk volume (OAR) is contoured as visualized on the planning CT scan. Applicable OARs will be contoured as clinically appropriate based on site treated.

5.5 Treatment Planning

- Any clinically acceptable, standard of care planning technique may be employed to deliver radiation to the index lesion, including 3D conformal treatment, intensity modulated radiation therapy, and stereotactic radiosurgery. Typically, patients should not be treated with two directly opposed beams due to the volume of tissue receiving high dose radiation, and using at least 3 beams or 2 non-opposed beams is encouraged. All plans are subject to review by the PI. All dose calculations will include corrections for tissue heterogeneities as specified by IROC Houston.

- Dose specifications: at least 95% of the target volume (PTV) is covered by at least 90% of the prescription dose.
- Critical Organ Doses: All standard of care critical organ dose-volume limits will be respected.

5.6 Radiation Quality Assurance Reviews

All patients treated on this protocol will undergo standard review in the Department of Radiation Oncology. At least two physicians will review the patient history, imaging findings, tumor contours, and radiation plan.

5.7 Radiation Toxicity

Toxicity will be graded based on CTCAE 4.0.

5.8 Criteria for Removal/Withdrawal from Treatment

Patients will be withdrawn from radiation treatment if their clinical conditions decline so they are no longer able to tolerate radiation, or are unlikely to clinically benefit from further therapy.

Patients will still receive follow up care per standard of care even if they withdraw from the study. If a subject withdraws consent to participate in the study or aspects of the study, attempts will be made to obtain permission to record at least survival data up to 6 months post-treatment. Details for withdrawal from immunotherapy is detailed below in section 6.1

6 Drug Therapy

Patients will pembrolizumab per standard of care. Prescribing information for pembrolizumab can be found at: https://www.merck.com/product/usa/pi_circulars/k/keytruda/keytruda_pi.pdf. Dose modification and discontinuation information can be found at: <https://www.keytruda.com/static/pdf/guide-for-keytruda.pdf>. Standard dosing is 200 mg fixed dose IV infusion every 3 weeks.

6.1 Duration of Therapy

Pembrolizumab therapy will continue until one or more of the following conditions are met:

- The subject withdraws consent.
- Confirmed radiographic disease progression
- Unacceptable adverse experiences
- Intercurrent illness that prevents further administration of treatment
- Investigator's decision to withdraw the subject
- The subject has a confirmed positive serum pregnancy test
- Noncompliance with trial treatment or procedure requirements
- The subject is lost to follow-up
- Administrative reasons

6.2 Pembrolizumab Supportive Care Guidelines

Subjects should receive appropriate supportive care measures per standard clinical care as deemed necessary by the treating oncologist. Suggested supportive care measures for the management of adverse events with potential immunologic etiology are outlined below. Where appropriate, these guidelines include the use of oral or intravenous treatment with corticosteroids as well as additional anti-inflammatory agents if symptoms do not improve with administration of corticosteroids. Note that several courses of steroid tapering may be necessary as symptoms may worsen when the steroid dose is decreased. For each disorder, attempts should be made to rule out other causes such as metastatic disease or bacterial or viral infection, which might require additional supportive care. The treatment guidelines are intended to be applied when the oncologist determines the events to be related to pembrolizumab.

- Pneumonitis:
 - For Grade 2 events, treat with systemic corticosteroids. When symptoms improve to Grade 1 or less, steroid taper should be started and continued over no less than 4 weeks.
 - For Grade 3-4 events, immediately treat with intravenous steroids. Administer additional anti-inflammatory measures, as needed.
 - Add prophylactic antibiotics for opportunistic infections in the case of prolonged steroid administration.
- Diarrhea/Colitis: Subjects should be carefully monitored for signs and symptoms of enterocolitis (such as diarrhea, abdominal pain, blood or mucus in stool, with or without fever) and of bowel perforation (such as peritoneal signs and ileus).
 - All subjects who experience diarrhea/colitis should be advised to drink liberal quantities of clear fluids. If sufficient oral fluid intake is not feasible, fluid and electrolytes should be substituted via IV infusion.
 - For Grade 2 or higher diarrhea, consider GI consultation and endoscopy to confirm or rule out colitis.
 - For Grade 2 diarrhea/colitis that persists greater than 3 days, administer oral corticosteroids.
 - For Grade 3 or 4 diarrhea/colitis treat with intravenous steroids followed by high dose oral steroids.
 - When symptoms improve to Grade 1 or less, steroid taper should be started and continued over no less than 4 weeks.
- Type 1 diabetes mellitus (if new onset, including diabetic ketoacidosis [DKA]) or \geq Grade 3 Hyperglycemia, if associated with ketosis (ketonuria) or metabolic acidosis (DKA)
 - For T1DM or Grade 3-4 Hyperglycemia
 - Insulin replacement therapy is recommended for Type I diabetes mellitus and for Grade 3-4 hyperglycemia associated with metabolic acidosis or ketonuria.
 - Evaluate patients with serum glucose and a metabolic panel, urine ketones, glycosylated hemoglobin, and C-peptide.
- Hypophysitis:
 - For Grade 2 events, treat with corticosteroids. When symptoms improve to Grade 1 or less, steroid taper should be started and continued over no less than 4

- weeks. Replacement of appropriate hormones may be required as the steroid dose is tapered.
- For Grade 3-4 events, treat with an initial dose of IV corticosteroids followed by oral corticosteroids. When symptoms improve to Grade 1 or less, steroid taper should be started and continued over no less than 4 weeks. Replacement of appropriate hormones may be required as the steroid dose is tapered.
 - **Hyperthyroidism or Hypothyroidism:** Thyroid disorders can occur at any time during treatment. Monitor patients for changes in thyroid function (at the start of treatment, periodically during treatment, and as indicated based on clinical evaluation) and for clinical signs and symptoms of thyroid disorders.
 - Grade 2 hyperthyroidism events (and Grade 2-4 hypothyroidism):
 - In hyperthyroidism, non-selective beta-blockers (e.g. propranolol) are suggested as initial therapy.
 - In hypothyroidism, thyroid hormone replacement therapy, with levothyroxine or liothyronine, is indicated per standard of care.
 - Grade 3-4 hyperthyroidism
 - Treat with an initial dose of IV corticosteroid followed by oral corticosteroids. When symptoms improve to Grade 1 or less, steroid taper should be started and continued over no less than 4 weeks. Replacement of appropriate hormones may be required as the steroid dose is tapered.
 - **Hepatic:**
 - For Grade 2 events, monitor liver function tests more frequently until returned to baseline values (consider weekly).
 - Treat with IV or oral corticosteroids
 - For Grade 3-4 events, treat with intravenous corticosteroids for 24 to 48 hours.
 - When symptoms improve to Grade 1 or less, a steroid taper should be started and continued over no less than 4 weeks.
 - **Renal Failure or Nephritis:**
 - For Grade 2 events, treat with corticosteroids.
 - For Grade 3-4 events, treat with systemic corticosteroids.
 - When symptoms improve to Grade 1 or less, steroid taper should be started and continued over no less than 4 weeks.
 - **Management of Infusion Reactions:** Signs and symptoms usually develop during or shortly after drug infusion and generally resolve completely within 24 hours of completion of infusion.

Table 2 below shows treatment guidelines for subjects who experience an infusion reaction associated with administration of pembrolizumab.

Table 2. Infusion Reaction Treatment Guidelines

NCI CTCAE Grade	Treatment	Premedication at subsequent dosing
Grade 1 Mild reaction; infusion interruption not indicated;	Increase monitoring of vital signs as medically indicated until the subject is deemed medically stable	None

intervention not indicated	in the opinion of the oncologist.	

Grade 2 Requires infusion interruption but responds promptly to symptomatic treatment (e.g., antihistamines, NSAIDS, narcotics, IV fluids); prophylactic medications indicated for < =24 hrs
	
Stop Infusion and monitor symptoms. Additional appropriate medical therapy may include but is not limited to:
 
 • IV fluids • Antihistamines • NSAIDS • Acetaminophen • Narcotics 
Increase monitoring of vital signs as medically indicated until the subject is deemed medically stable in the opinion of the oncologist. If symptoms resolve within one hour of stopping drug infusion, the infusion may be restarted at 50% of the original infusion rate (e.g., from 100 mL/hr to 50 mL/hr). Otherwise dosing will be held until symptoms resolve and the subject should be premedicated for the next scheduled dose.
 
Subjects who develop Grade 2 toxicity despite adequate premedication should be permanently discontinued from further trial treatment administration.
	
Subject may be premedicated 1.5h (±30 minutes) prior to infusion of pembrolizumab with:
 
 • Diphenhydramine 50 mg po (or equivalent dose of antihistamine). • Acetaminophen 500-1000 mg po (or equivalent dose of antipyretic).

Grades 3 or 4 Grade 3: Prolonged (i.e., not rapidly responsive to symptomatic medication and/or brief interruption of infusion); recurrence of symptoms following initial improvement; hospitalization indicated for other clinical sequelae (e.g., renal impairment, pulmonary infiltrates)
 
Grade 4: Life-threatening; pressor or ventilator support indicated
	
Stop Infusion. Additional appropriate medical therapy may include but is not limited to:
 
 • IV fluids • Antihistamines • NSAIDS • Acetaminophen • Narcotics • Oxygen • Pressors • Corticosteroids • Epinephrine 
Increase monitoring of vital signs as medically indicated until the subject is deemed medically stable in the opinion of the oncologist. Hospitalization may be indicated.
 
Subject is permanently
	
No subsequent dosing

	discontinued from further trial treatment administration.	
Appropriate resuscitation equipment should be available in the room and a physician readily available during the period of drug administration.		

7 Adverse Event Reporting Requirements

7.1 Adverse Event (AE) Reporting

An AE is any undesirable sign, symptom or medical condition or experience that develops or worsens in severity after starting the first dose of study treatment or any procedure specified in the protocol, even if the event is not considered to be related to the study. Abnormal laboratory values or diagnostic test results constitute AEs only if they induce clinical signs or symptoms or require treatment or further diagnostic tests.

AEs of Grade 3 and above (per CTCAE v4.0) will be monitored and recorded in study-specific case report forms (CRFs) in the REDCap system from the time of the first study treatment through 30 days following the end of study treatment, or until the patient receives an alternative anti-cancer therapy, whichever date comes first. AEs related to tumor biopsies that are done solely for research will be monitored, recorded, and reported according to the same standards.

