Example 5	iUPD	iSD	iSD, iUPD, or NE	iSD, iUPD, iCPD, or NE	iSD, iUPD, iCPD, or NE	iSD
Example 6	iUPD	iCPD	Any	Any	Any	iCPD
Example 7	iUPD	iUPD (no iCPD)	iCPD	Any	Any	iCPD
Example 8	iUPD	NE	NE	NE	NE	iUPD

Eight examples are presented for patients with target disease at baseline, but many more scenarios exist following the same principles. Table assumes a randomised study in which confirmation of complete response or partial response is not required. For patients with non-target disease only at baseline, only iCR or non-complete response or non-progression of disease can be assigned at each timepoint (not shown in the table for ease of presentation). "I" indicates immune responses assigned using iRECIST. iBOR=best overall response. iCR=complete response. iPR=partial response. NE=not evaluable. iUPD=unconfirmed progression. iCPD=confirmed progression. iSD=stable disease. RECIST=Response Evaluation Criteria in Solid Tumours.

Table 3: Scenarios of assignments of best overall response using iRECIST

Secondary Objectives:

- Progression free survival.
- Overall survival.
- Safety and tolerability as evaluated by the incidence, severity, duration, causality, seriousness, and type(s) of adverse events as assessed by CTCAE version 4.0

Exploratory Objectives:

- Changes in peripheral blood immune cell subpopulations measured via multi-parameter flow cytometry:
 - Important T-cell subsets using markers such as: CD3/CD8/CD4/Foxp3/CD45RA/CD45RO/CCR7/CD28/CD27/CD57/CD25/HLA-DR/CTLA4/PD-1
 - NK cells will be assessed using CD16/CD56/CD69.
 - B-cells and dendritic cells will be analyzed using: CD19, CD123, CD11c, CD86, MHC class I and II, CD70, and CD54.
 - MDSC will be assessed using: CD11b, CD 14, CD33.
- Next generation sequencing of the T-cell receptor- β locus in genomic DNA from sorted CD4+ and CD8+ T cell subsets from blood samples using the TRB ImmunoSeq kit (Adaptive Biotechnologies).
- Tumor biopsies (pre- and post-treatment of a non-radiated site) in select patients who consent will be assessed for: cell death, tumor infiltrating lymphocytes, expression of cell surface markers including HLA, PDL1, etc., and undergo multiparameter flow cytometry as well as TCR sequencing.

3 Study Design

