Time points for peripheral blood collection are based on prior studies, including Huang *et al.* and Twyman-Saint Victor *et al.* described above^{9,29}, that show peak changes in peripheral blood immune cell populations around 3-6 weeks post start of therapy for checkpoint inhibitor immunotherapy, and changes after radiation treatment that peak around 2-4 weeks but can persist for months after treatment.

After the study period as outlined above, all patients will be followed at least once every 3 months by the treating oncologist per standard of care. Toxicity, disease response, and survival will be recorded at each clinic visit. Patients are considered off-study once disease progression is detected per iRECIST³⁰. Follow up with radiation oncology is not required but records will be obtained from treating oncologist. All correlative studies will be batched for analysis.

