3.2. Statistical Plan

This is a single-arm phase 2 study with the primary endpoint of overall response rate per iRECIST. Overall response rate will be calculated as the percentage of patients achieving a PR or CR, and will be presented along with the 95% CI. Historical data suggest a response rate of 20%, and we hypothesize a true response rate of 40% with the proposed treatment. With 20 patients, we'll have 80% power to observe an estimated response rate that is statistically significantly higher (at the one-sided significance level of .05) than the fixed rate of 20%. Secondary endpoints overall and progression-free survival will be estimated using the method of Kaplan and Meier with 95% CI obtained using Greenwood estimates of variance. Toxicities as assessed by CTCAE version 4.0 will be summarized as the proportion of patients with such toxicities, in addition to total number of toxicities (allowing for multiple toxicities within a patient) among all patients. The exploratory endpoints, change in peripheral blood cell populations will be assessed by estimating the average change between pre- and post-treatment, and these differences will be calculated for each time point; the one-sample t-test will be used to test the null hypothesis that the change is equal to zero. Trends for changes in differences from pre-treatment to post-treatment across time will be assessed using generalized linear models. Similar methods will be used to assess change in tumor biopsies for patients who consent to such analyses, where changes from pre- to post-treatment will be examined for cell death, tumor-infiltrating lymphocytes and expression of various cell-surface markers.

Should this regimen be deemed to be potentially efficacious as defined above, consideration will be given to conduct a subsequent randomized study designed to compare neutron radiation plus checkpoint inhibitors versus checkpoint inhibitors alone.

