8.2 Interim Data Review

Interim reports with statistical analyses will be prepared twice per year until the initial treatment results have been presented or published. In general, the interim reports will contain the following information:

- Patient accrual rate with a projected completion date (while the study is still accruing)
- Total patients accrued
- Frequencies and severity of adverse events
- Compliance rates of treatment delivery

Institutional support of trial monitoring will be in accordance with the FHCRC/University of Washington Cancer Consortium Institutional Data and Safety Monitoring Plan. Under the provisions of this plan, FHCRC Clinical Research Support (CRS) coordinates data and compliance monitoring conducted by consultants, contract research organizations, or FHCRC employees unaffiliated with the conduct of the study. Independent monitoring visits occur at specified intervals determined by the assessed risk level of the study and the findings of previous visits per the institutional DSMP.

In addition, protocols are reviewed at least annually and as needed by the Consortium Data and Safety Monitoring Committee (DSMC), FHCRC Scientific Review Committee (SRC) and the FHCRC/University of Washington Cancer Consortium Institutional Review Board (IRB). The review committees evaluate accrual, adverse events, stopping rules, and adherence to the applicable data and safety monitoring plan for studies actively enrolling or treating subjects. The IRB reviews the study progress and safety information to assess continued acceptability of the risk-benefit ratio for human subjects. Approval of committees as applicable is necessary to continue the study.

The trial will comply with the standard guidelines set forth by these regulatory committees and other institutional, state and federal guidelines.

9 Data Management/Confidentiality

The investigator will ensure that data collected conform to all established guidelines. Each subject is assigned a unique patient number to assure subject confidentiality. Subjects will not be referred to by this number, by name, or by any other individual identifier in any publication or external presentation. The licensed medical records department, affiliated with the institution where the subject receives medical care, maintains all original inpatient and outpatient chart documents.

Subject research files are stored in a secure place (or database). Access is restricted to authorized personnel.

References

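### Only adverse events of Grade 3 and above are committed to the case report forms, while the safety objective and the toxicity summaries carry no grade limit

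*Combined protocol and SAP*

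**What the plan says.** **Collection.** Section 7.1 defines an adverse event without reference to grade, then narrows what reaches the forms: "AEs of Grade 3 and above (per CTCAE v4.0) will be monitored and recorded in study-specific case report forms (CRFs"). The window opens at the first study treatment. It closes 30 days after study treatment ends, or when another anti-cancer therapy starts if that is sooner.

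**Objective and analysis.** Section 2 lists as a secondary objective "Safety and tolerability as evaluated by the incidence, severity, duration, causality, seriousness, and type(s) of adverse events". Section 3.2 says "Toxicities as assessed by CTCAE version 4.0 will be summarized as the proportion of patients with such toxicities", and adds the "total number of toxicities (allowing for multiple toxicities within a patient) among all patients". None of these carries a grade limit.

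**Follow-up.** For the period after the scheduled study visits, section 3.1 says "Toxicity, disease response, and survival will be recorded at each clinic visit".

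**Causality.** Section 7.2 first says that events are assessed against the treatment or procedure the patient received. It then asks the investigator to document the relationship to study medication, on four levels (unrelated, possible, probable, definite) that each refer to the investigational agent(s). Section 8.1 stops the trial for any Grade 5 event, or two or more Grade 4 events, within 30 days after treatment ends and rated at least possibly related to radiation.

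**The concern.** A reader of sections 2 and 3.2 would expect safety results for all grades. The data that 7.1 commits the trial to collect cannot provide them, and nothing in 3.2 tells the analyst or the reader that the results stop at Grade 3.

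Tolerability is part of the stated objective, and lower-grade events bear on it by the protocol's own account. Section 7.2 names fatigue and skin reaction in the field as typical of the radiation, without giving grades. Section 6.2 suggests corticosteroids for several Grade 2 immune events; for pneumonitis it says "For Grade 2 events, treat with systemic corticosteroids". Table 2 links one Grade 2 infusion reaction to permanent discontinuation. None of these reaches the 7.1 threshold.

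The causality wording matters for a different reason. Two treatments are given together and the stopping rule counts events attributed to one of them. A single rating tied to the agents does not clearly show which events the rule should count.

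**Working it through.** The plan gives no figure to reproduce here, so the check compares the text of the sections.

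**Step 1: grade range, place by place.**

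| Place | What it covers | Grade range stated |
|---|---|---|
| 7.1, definition | what counts as an adverse event | none |
| 7.1, recording | events entered on the forms | Grade 3 and above |
| 2, secondary objective | safety and tolerability | none |
| 3.2 | proportion of patients with toxicities; total toxicities | none |
| 3.1, later follow-up | toxicity noted at clinic visits | none; no form or event attributes named |
| Study calendar | scheduled assessments | no toxicity or adverse event row |

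The commitment in 7.1 covers Grades 3, 4 and 5, which is 3 of the 5 grades. The objective and section 3.2 are unrestricted.

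**Step 2: does another section fill the gap?** Section 3.1 is the only candidate. It concerns visits after the study period, and specifies neither a grade range nor a form. It also does not mention duration, causality or seriousness, which the objective requires. Low-grade events may be noted in clinic records under it, but it does not ensure that they become analysable data.

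**Step 3: what falls below the threshold.** Section 6.2 has 7 immune headings: pneumonitis, diarrhea/colitis, type 1 diabetes/hyperglycemia, hypophysitis, thyroid, hepatic and renal.

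- Corticosteroids are clearly attached to Grade 2 under 4 of them: pneumonitis, diarrhea/colitis (if it lasts more than 3 days), hypophysitis and renal.
- The hepatic corticosteroid line is a separate bullet following the Grade 2 bullet. Whether it belongs to Grade 2 depends on the layout, so the firm count is 4 of 7, or 5 of 7 if it does.
- Table 2 adds one case: a Grade 2 infusion reaction despite premedication, which leads to permanent discontinuation.

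**Step 4: causality.** All 4 levels in 7.2 refer to investigational agent(s), and 0 of 4 name radiation. The study summary calls both treatments standard of care, so the term does not clearly point to the radiation. The labels in 8.1 match the upper three levels in 7.2, but are applied to radiation by name. Section 7.2 therefore does not specify a separate recorded rating for the quantity that 8.1 counts.

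**Step 5: what is not affected.** Grades 4 and 5 lie inside the 7.1 range. Section 8.1 also has Grade 3 events reported to the principal investigator within 48 hours, and higher grades within 24 hours. The primary endpoint is response and uses none of these data.

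**The case against.** The strongest reply is that collecting only Grade 3 and above is a legitimate choice when both treatments are described as standard of care. Section 3.2 could be read as summarising whatever 7.1 collects. Proportions and totals can indeed be computed from Grade 3+ data, so the inference that 3.2 cannot be carried out at all goes too far. What stands is that the restriction is unstated, and that the objective names tolerability without a limit.

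A reader might also count two further sections as conflicting. Section 5.7 says "Toxicity will be graded based on CTCAE 4.0", which only sets a grading scale. The interim report item in 8.2, "Frequencies and severity of adverse events", can be met with Grade 3 to 5 data. Neither adds to the problem.

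On causality, a reader might infer that the stopping rule cannot be operated. The documents do not support that. The general sentence in 7.2 about treatment or procedure can include radiation, 8.1 names radiation explicitly, and every Grade 3+ event goes to the principal investigator, whose department is radiation oncology. The forms themselves are not in the documents, so a radiation field may already exist. What remains is loose wording in 7.2 and no specified separate rating.

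It is also fair to say that all-grade collection is not free. Section 7.1 counts events whether or not they are related, so low-grade symptoms of advanced cancer would be entered too.

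**Conclusion.** The mismatch is real and worth correcting. As written, the section 3.2 toxicity summaries would describe Grades 3 to 5 while the objective and the analysis text imply all grades. The omitted events include any Grade 1 or 2 radiation effects, Grade 2 immune events under at least 4 of 7 headings where corticosteroids are suggested, and the Grade 2 infusion reaction linked to discontinuation. The causality wording is a secondary point: the rule in 8.1 can be applied, but 7.2 does not specify the recorded input it needs.

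The conclusion rests on the protocol text alone and assumes that the forms follow it. With no event rates in the documents, the number of events or patients left out cannot be estimated. Nothing here weakens Grade 3+ safety reporting.

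**What to change.** **Grade scope, one of two options.**

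1. In 7.1, record adverse events of all grades on the forms. Name the treatment whose end closes the window, because the workload depends on it: radiation must finish within 2 weeks (5.1), whereas pembrolizumab continues until a condition in 6.1 is met. The existing 24- and 48-hour reporting to the principal investigator stays as it is. The cost is more data entry for about 20 patients, including low-grade disease symptoms. Some entries would come from oncology records, since non-radiation appointments may take place at either of two sites (section 5).
2. Keep the Grade 3 cut-off, and state in sections 2 and 3.2 that safety conclusions are limited to Grade 3 and above. This is a text change only, at the price of not reporting lower-grade tolerability.

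**Causality.** In 7.2, record the relationship separately for neutron radiation and for pembrolizumab on the same four-level scale, so that 8.1 has a recorded input. This needs at most one extra field per event, and none if the forms already hold it.

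No new visits or procedures are required.
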